# 4.6 Vulnerable Populations

Population protected under HHS regulations 45CFR46 Subparts B, C, & D Study Procedures: Participants who are pregnant at the time of baseline assessments will not be eligible for the study.

Populations vulnerable to undo influence or coercion: Educationally or economically disadvantaged persons are included but not solely targeted for recruitment. Cognitively impaired persons are not included in the current study. All the participants will be drug-dependent individuals. They are considered a vulnerable population due to the risks, both perceived and real, created through the use of illegal drugs. Care will be taken to ensure that they are treated with respect and consideration throughout the study process.

# 4.7 Study Procedures

See Table below for a schedule of study procedures.

P.S. = pre-screening day;

\* The mobile team (i.e. nurse practitioner, case manager, recovery specialist) will have contact with each participant at least 3 times per week.

# 4.8 Participant Screening

# 4.8.1 Subject recruitment

The recruitment of participants for this study will be accomplished using a community awareness campaign involving street outreach, targeted social media, and local advertisement. This campaign will begin one month before activation of the rapid induction intervention. During this time, the mobile assessment team will begin to be present in the designated location where we will park the Mobile Clinical Trials Unit (MCTU).

The MCTU is a medical vehicle is built on a heavy-duty truck frame that contains an expandable waiting area and two private examination rooms. It is approved for use by the Pennsylvania Department of Health as a site for HIV testing and the exam rooms provide comfortable and private space for counseling, interviews, and data and specimen collections. The selection of parking locations for the MCTU is an important process and will be informed

by issues of access to the target population, data regarding recent overdoses, and community support and permission. We will work with the staff of Prevention Point that has an extensive access to the neighborhood to define the best locations within the neighborhood.

## 4.8.2 Participant Education and the Informed Consent Process

Potential participants who express interest in initiating treatment will be engaged in a structured approach to education about the study and its procedures. The information delivered at this point will be supportive and motivational and describe study participation as an opportunity to consider options for treatment. It will also be explained that their participation can contribute to a better understanding of the most effective ways to assist individuals who want to begin treatment. Staff will make it clear that even if they do not become engaged in treatment, their experiences are important and their contributions to the research will be valuable. We will inform participants that their direct involvement in the project will last for one year and that we will want to contact them at scheduled assessment visits regardless of their treatment status. This discussion will offer potential participants a chance to ask questions and receive prepared materials explaining the study and the requirements for participation.

Those who appear to be eligible and express interest will begin the informed consent process to allow for screening. The informed consent process will give the participant an accurate understanding of the research procedures and make it clear that participation is voluntary. The informed consent document will be read and reviewed with the participant. The consent form includes clear language with special attention to the provision of permissions to contact the participant and individuals they identify as acceptable contacts if we are unable to make direct contact with the participant for the 1- and 6-month assessments. Since we will also need to confirm subsequent treatment engagement, the consent form will include permission to contact treatment providers to determine treatment status as well as permission for the Philadelphia Department of Public Health to look shared information about their subsequent use of health department services (CARES database. http://www.phila.gov/hhs/data/Pages/Cares.aspx). The consent form will also include a statement indicating that research staff will submit their names to the National Death Index for a record search should we be unable to make contact for a 90-day period.

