# 1 Study Summary

Title	Rapid initiation of buprenorphine/naloxone to optimize MAT utilization in Philadelphia		
Short Title	Rapid initiation of BUP/NX		
Study overview	The proposed research will evaluate the ability of a mobile, rapid induction procedure to engage individuals in ongoing medication assisted treatment. A total of 250 untreated ndividuals meeting criteria for opioid use disorder and at high risk of opioid overdose will be enrolled in the study. Recruitment will take place in two targeted neighborhoods of Philadelphia (Kensington and South Philadelphia) with a high prevalence of fatal and non- fatal opioid overdose. A total of 250 participants will be engaged in the research. Following nformed consent and determination of eligibility, 125 individuals will be enrolled as they engage with the mobile, rapid induction team and 125 individuals will be enrolled as they seek treatment from the CRC Episcopal Hospital (serving Kensington area) or BAC/CRC Hall Mercer Community Mental Health (serving South Philadelphia). The intervention group will receive four weeks of treatment with buprenorphine /naloxone and support for treatment engagement provided by a case manager and a peer recovery specialist. All participants will be assessed at baseline and then 1- and 6-month following enrollment. The primary endpoint for the study is continued enrollment in medication-assisted treatment at 6 months post enrollment.		
Study Duration	The estimated duration of study is 36 months. Individual study subject participation will last 6 months.		
Study Center(s)	The University of Pennsylvania will serve as the primary project location, and all recruitment and data collection efforts will be executed by University of Pennsylvania staff members. A subcontract has been established with Prevention Point Philadelphia and Public Health Management Corporation.		

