## 3.7 Study Measures

All interviews will be administered by experienced research assistants trained in the administration of the proposed assessments. Following confirmation of eligibility, the mobile research assistants will complete the baseline assessment (described below). The participant assessments in this research will be sharply focused on the valid and reliable measurement of its primary endpoints i.e. ongoing treatment engagement will be the primary endpoint on which the study is powered. We will also carefully compare the two groups with respect to the rate of continued opioid use and subsequent overdoses. All assessments will be completed by trained research staff (not clinicians) at baseline, and again at 1- and 6-month post-enrollment. We anticipate follow-up rates of 95% and 90% at Month 1 and 6, respectively. We anticipate that the assessments will take approximately 45 minutes to complete.

- Physical history and examination including a blood test to evaluate the liver function.
- Locator Data Collection: A detailed contact sheet (Locator Form) will be completed for all subjects as part
  of the baseline assessment. We will ask participants to provide contact information on themselves and at
  least three additional people with whom they are most likely to stay in contact. We will also ask about other
  places where participants might be able to be contacted in the future. Participants will provide consent for
  research staff to contact individuals whose contact information they provide. Contact information will also
  include e-mail addresses and mobile phone numbers for texting. The locator form will be updated at each
  scheduled assessment visit. In addition, participants will be asked to call or visit the research staff
  whenever they have updates to provide regarding changes in contact information.
- DSM-5 Substance Use Disorder Checklist: This form is a listing of the eleven DSM-5 criteria for substance use disorder. We will screen for opioids, cocaine, and alcohol as each are necessary for confirmation of inclusion and exclusion criteria. A score of 4-6 is considered moderate severity and from 7-11 is considered severe substance use disorder. An opioid use disorder score of 4 or greater will be required for study eligibility. Alcohol use disorder and benzodiazepine scores of 4 or greater will be exclusionary.
- A study specific questionnaire that includes:

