# 4 Study Population and Duration of Participation

#### 4.1 Duration of Study Participation

The duration of study participation including screening/baseline assessments to follow-up will be 6 months.

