# 4.4 Exclusion Criteria

- Inability to comprehend or complete study procedures
- Plans to relocate during study time frame
- Currently in medication assisted treatment (MAT) for substance use disorder
- Evidence of serious liver disease (LFTs > 3 x the upper limit of normal)
- Pregnancy or lactation
- Moderate to severe alcohol or benzodiazepine use disorder

There will be no exclusion based on gender or race/ethnicity. The participants to be recruited are expected to reflect the demographics of previous data provided by Philadelphia Department of Health on individuals who overdosed in the city of Philadelphia. Both men and women will be recruited for this study as both are affected by opioid epidemics. No gender restrictions are to be followed at recruitment. According to the available data, we are expecting enrolling about 30% of females. Minority populations will not be excluded. We are expecting enrolling about 59% European-American/non-Hispanic, 25% African-American/non-Hispanic, 15% of Hispanic/Latino, and 1% of Native American.

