## 4.10 Subject Withdrawal

Participants may choose to withdraw from the study at any time. They do this by providing verbal or written communication to this effect. Withdrawal from the study will not impact access to care. The Principal Investigator may withdraw subjects for reasons related to safety or for administrative reasons. It will be documented whether or not each subject completes the study. Subjects who do not complete the intervention will continue to be contacted to complete follow-up visits (Month 1 and 6) to collect final evaluations and assess adverse events.

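### Section 4.8.2 has staff tell candidates that involvement lasts one year, although the stated participation period and the scheduled visits end at 6 months

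*Combined protocol and SAP*

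**What the plan says.** Section 4.8.2 describes a structured education step that comes before the consent document is read. Staff are to tell potential participants that "their direct involvement in the project will last for one year", and that they will be contacted for scheduled assessments whether or not they are in treatment.

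Other sections give a different duration:

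- Study Summary: "Individual study subject participation will last 6 months".
- Section 4.1: "The duration of study participation including screening/baseline assessments to follow-up will be 6 months".
- Section 3.7: assessments are completed "at baseline, and again at 1- and 6-month post-enrollment".
- Section 4.10: people who do not complete the intervention are still followed at months 1 and 6, and those visits supply the final evaluations.
- Section 10.3: payments are made at baseline, week 4 and week 24.
- Section 4.8.2 itself: the permission to use alternative contacts applies "if we are unable to make direct contact with the participant for the 1- and 6-month assessments".

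Separately, section 4.4 excludes people with "Plans to relocate during study time frame" and does not define that time frame. The Study Summary also gives a duration for the project as a whole: "The estimated duration of study is 36 months".

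**The concern.** The one-year figure is an instruction about what candidates are to be told, so it will be acted on as written. How long a study lasts is basic to a decision about joining it. The paragraph that follows in 4.8.2 undertakes that consent will leave participants with a correct understanding of the procedures, and section 4.6 describes the study population as vulnerable.

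The error overstates the commitment. Nobody would undergo more visits than they had been told of, but some eligible people might decline a study that they believe is twice as long as it is. The documents give no basis for estimating how many.

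**Working it through.** No modelling is needed. The check is whether the last scheduled participant contact falls at 6 months or at one year.

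**1. The plan's own figure.** Section 4.1 gives 6 months from screening/baseline to follow-up. Compare the last contact in each place that sets one:

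| Source | Last contact |
|---|---|
| 3.7 Study Measures, assessments | month 6 |
| 4.9.1, comparison group assessments | month 6 |
| 4.10 Subject Withdrawal, final evaluations | month 6 |
| 10.3 Subject Compensation, last payment | week 24 |
| 4.8.2, contact permissions | 6-month assessment |

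Week 24 in months is 24 × 7 / 30.4375 = 5.5, which fits a month-6 visit. The payment table closes on three visits: 3 × $30 = $90 and 3 × $5 = $15, both matching its stated totals. No later paid visit has dropped out of it. The 6-month figure is reproduced.

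**2. The one-year figure.** 12 / 6 = 2, so the statement doubles the planned duration. Months 7 to 12 contain no assessment and no payment in any of these sections. The schedule table in section 4.7 was not legible in the text available and is not relied on here.

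**3. Could the overall timeline support one year?** Section 3.6 starts the intervention in month 6 and runs it for 18 months, so enrollment ends at about month 24. Follow-up would then end at:

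- 24 + 6 = month 30 with 6 months of participation;
- 24 + 12 = month 36 with one year.

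Both fit within the 36-month study. The timeline does not discriminate between them, but the visit schedules do.

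**4. Could records follow-up account for it?** Use of the CARES service records (section 3.8.1) and the National Death Index search (section 4.8.2) are passive. The 4.8.2 sentence speaks of direct involvement and links it to scheduled assessments. Adding the 90 days without contact that trigger the death search to month 6 gives about 6 + 3 = 9 months, which is still not 12.

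**5. Effect on the statistics.** The section 5.2 calculation uses 125 per group, 80% completers, a within-subject correlation of 0.3, 25% against 40% engaged, and outcomes at months 1 and 6. None of these inputs depends on involvement after month 6, so nothing changes.

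**The case against.** The strongest reply is that this is a slip of a few words in the education talk, and that it may never reach the consent document. That document is read and reviewed afterwards, and what 4.8.2 reports of it refers to the 1- and 6-month assessments. The form was not available, so it cannot be said that signed consent repeats the error. This stands, and it limits the claim to what candidates are told beforehand. It does not excuse an instruction to tell them the wrong figure.

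Two stronger readings are tempting, and the documents support neither.

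- **Relocation.** A reader might infer that the one-year statement changes who is excluded for planning to move. The exclusion refers to an undefined study time frame and is not linked to 4.8.2. It could be read as 6 months, one year or 36 months. People planning to move in months 7 to 12 would be affected only if staff took the window from the education talk, which nothing says they do. The ambiguity would remain after 4.8.2 was corrected.
- **Difference between groups.** Because separate staff recruit the mobile and BAC/CRC participants, a reader might infer that one team would use 12 months and the other 6. Both work under one protocol with one set of criteria, and section 4.9.1 gives the comparison group the same assessment times. Nothing assigns the teams different durations.

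**Conclusion.** The instruction in 4.8.2 is wrong as written. It states one year where the summary and section 4.1 state 6 months, and the assessments, final evaluations, payments and contact permissions all stop at month 6 or week 24. Followed literally, it would give candidates twice the planned duration before they consent.

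This rests on the sections named above being the intended schedule. They agree with one another, and one year as a length of participation appears only in 4.8.2. Any effect on willingness to enroll is possible but cannot be sized from the documents. An effect on relocation exclusions or on the balance between groups is not established. Endpoints, sample size, power and analysis are untouched, so this is a minor correction, though a clear one.

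**What to change.** In section 4.8.2, change the stated duration from one year to 6 months. Check the consent form and the prepared participant materials for the same figure and correct them if it appears. If enrollment has begun, establish what participants have been told.

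As a separate clarification, define the relocation window in section 4.4 and in the Study Summary criteria as the 6-month participation period, counted from enrollment.

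The cost is wording only, plus whatever review the IRB requires for a protocol text change. No visit, data item or analysis changes.

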# 3.2 Innovation

Rapid induction with buprenorphine/naloxone in the community is the core innovation of the proposed research. By reducing time and geographic barriers to treatment and the control of withdrawal symptoms, the intervention will provide a one-month opportunity to link participants to an appropriate, ongoing treatment provider. This use of MAT is an innovation designed to minimize common barriers to treatment engagement. The use of buprenorphine will also allow for the transition to other MAT strategies that may be more appropriate for the individual, including methadone maintenance treatment, buprenorphine treatment, or treatment with extended-release naltrexone. The ability to engage individuals with opioid use disorder in their home environment is another important innovation of the proposed research. The mobile engagement team will include a Nurse Practitioner, a Case manager, and a Certified Peer Recovery Specialist and will begin inductions on the mobile medical unit or in the individual's home. The mobility of the team is an innovation allowing easy access to individuals who indicate interest in treating their opioid use disorder. We will assess treatment status at six months post enrollment as our primary outcome measure. With the permission of the participant, the CARES Integrated Data Systems Service Utilization database will be available to identify involvement with drug treatment and other services provided by the City prior to and following the enrollment in the study.

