# 3.8 Study Endpoints

# 3.8.1 Primary end-point

Treatment engagement is the primary endpoint in this study.

- Confirmation of enrollment in MAT: Assessments will collect self-report of participation in MAT at the time
  of assessment as well as during the intervening time-period. We will also collect confirmatory
  documentation from the identified treatment provider. Permission to contact the treatment provider will be
  included in the consent and a specific release of information form signed by the participant will be included
  in the request for confirmation.
- CARES Integrated Data Systems Service Utilization: Participants enrolled in this study will provide consent to allow the Health Department to review their records of utilization of city services prior to and following enrollment in the study.

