## Comparison group – Treatment as usual

During the same period of time, participants will also be recruited at the City of Philadelphia Behavioral Health System Behavioral Assessment Centers (BAC) and Crisis Response Centers (CRC) located at Episcopal Hospital serving Kensington area and Hall Mercer BAC/CRC (a University of Pennsylvania program) serving South Philadelphia area. Two research assistants from the TRI-PHMC will enroll and follow-up 125 participants at BAC/CRC. The participants will complete the same assessments at baseline, 1- and 6-month follow-up. Authorization for the Philadelphia Department of Public Health to look shared information about their subsequent use of health department services (CARES database, http://www.phila.gov/hhs/data/Pages/Cares.aspx) will also be requested in the consent form. Research staff will only conduct assessments. Treatment engagement services will be provided by the staff of the BAC/CRC as usual.

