# 5.2 Sample Size and Power Determination

Our power analysis has been based on this primary aim. Our primary hypothesis is that participants who received rapid induction will more likely be engaged in ongoing treatment at 1- and 6-month follow-up than participants who sought treatment at BAC/CRC. We will test this hypothesis at a 5% level of significance. Our principal interest is in the comparison of engagement rates between the mobile intervention and BAC/CRC groups, at months 1 and 6. Preliminary data suggest an engagement rate of about 20-30% in the BAC/CRC group. Assuming a steady loss to attrition that yields 80% completers, and a within-subject correlation of 0.3, the methods of Diggle et al. (Diggle, Heagerty et al. 2002) show that our sample size of 125 in each group yields 80% power for differences of about 15% in engagement rates between the two groups (e.g., 80% power for BAC/CRC: 25% vs. Mobile: 40%, corresponding to a RR=1.6 and an OR=2.0)

**Propensity score model to account for non-randomized allocation:** The participants are not randomly assigned to the mobile rapid induction intervention and BAC/CRC groups, so it is possible that there will be confounding of the group effect with the effects of characteristics of the participants. We will use a propensity score approach (Rosenbaum 2002, Rothman, Greenland et al. 2008) to account for this. We will use a broad range of baseline variables as covariates in a logistic regression model predicting treatment group, including age, race/ethnicity, gender, number of previous overdoses, number of previous treatments for opiate use disorder, type of opioid used, and depression. The model will yield predicted probabilities of BAC/CRC group for all participants (the propensity score), and we will create a five-level ordinal variable based on the quintiles of the propensity score. We will then include this ordinal variable as a stratum variable in our models.

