#### 8.4 Informed Consent Process / HIPAA Authorization

Subjects will hear a study description where all study procedures, risks, and information about the study medication will be reviewed. Subject questions will be answered. Following this presentation, the combined informed consent and HIPAA form will be completed by participants.

Information about study subjects will be kept confidential and managed according to the requirements of the Health Insurance Portability and Accountability Act of 1996 (HIPAA). Those regulations require a signed subject authorization informing the subject of the following:

- What protected health information (PHI) will be collected from subjects in this study
- Who will have access to that information and why
- Who will use or disclose that information
- The rights of a research subject to revoke their authorization for use of their PHI.

In the event that a subject revokes authorization to collect or use PHI, the investigator, by regulation, retains the ability to use all information collected prior to the revocation of subject authorization. For subjects that have revoked authorization to collect or use PHI, attempts should be made to obtain permission to collect at least vital status (i.e. that the subject is alive) at the end of their scheduled study period.

The following personal health information will be collected as part of this study:

- 1. Name
- 2. Address
- 3. Date of Birth
- 4. Phone number(s)
- 5. Electronic mail address

6. Dates of procedures and events (such as hospital admissions and discharges) relevant to side effect and adverse event reporting

The following individuals and organizations may use or disclose personal health information:

- The Principal Investigator (PI) and research staff
- The Philadelphia Department of Public Health Institutional Review Board
- The University of Pennsylvania Office of Regulatory Affairs
- The University of Pennsylvania Office of Human Research (the office that monitors research studies)

The Principal Investigators or research staff will inform participants if there are any changes to the list above during their active participation in the trial.

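### The permission for City service records (CARES) is described with two different time spans, and the pre-enrollment records have no stated role in the confounding adjustment

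*Combined protocol and SAP*

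**What the plan says.** Four places describe access to City records.

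- Section 3.8.1 (primary endpoint): participants "will provide consent to allow the Health Department to review their records of utilization of city services prior to and following enrollment".
- Section 3.2 (Innovation): with the participant's permission, CARES will show drug treatment and other "services provided by the City prior to and following the enrollment in the study".
- Section 4.8.2 (consent process): the form will include "permission for the Philadelphia Department of Public Health to look shared information about their subsequent use of health department services".
- Section 4.9.1 (Comparison group – Treatment as usual): the consent form will request authorization for the Department to "look shared information about their subsequent use of health department services".

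Section 8.4 introduces a list with "The following personal health information will be collected as part of this study". The list holds contact identifiers, date of birth, and dates of procedures and events tied to adverse event reporting. It names no service-use records for any period.

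Section 5.2 adjusts for non-random allocation with a propensity score entered as quintile strata. Its named covariates include age, race/ethnicity, gender, previous overdoses, and "number of previous treatments for opiate use disorder, type of opioid used, and depression". Section 3.4 names a similar set and ties it to the study assessments. Neither section mentions CARES. Among the exclusions in Section 4.4 is "Currently in medication assisted treatment (MAT) for substance use disorder", so only present treatment is barred.

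**The concern.** There are two linked problems.

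The first is the scope of consent. A form drafted from Section 4.8.2 and the comparison-group text would authorize records from enrollment onward. A form drafted from Section 3.8.1 would authorize both periods. If the narrower form is used, the earlier records can be recovered only by re-consent. Section 5.2 itself allows for 80% completers, so 250 × 0.20 = 50 participants could be out of reach by month 6. On the 90% month-6 follow-up in Section 3.7 the figure is 250 × 0.10 = 25.

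The second is what the records would be for. Comparison participants are recruited at the BAC/CRC, which Section 2.4 calls the City's point of entry into MAT. Mobile participants contact an outreach team after a community campaign (Sections 3.5.1 and 4.5). Recent contact with City treatment could well differ between the groups and could predict whether a MAT slot is taken up. Someone who left MAT shortly before enrollment is eligible. A lifetime count of treatments does not separate that person from someone last treated years ago. The plan proposes to obtain records that could make this distinction, yet assigns them to no analysis.

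**Working it through.** **Step 1. Set the passages side by side.**

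| Place | Period covered | Services named |
|---|---|---|
| 3.8.1 Primary end-point | before and after enrollment | City services |
| 3.2 Innovation | before and after enrollment | drug treatment and other City services |
| 4.8.2 Consent process | subsequent only | health department services |
| 4.9.1 Comparison group | subsequent only | health department services |
| 8.4 Authorization list | none stated | none stated |

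The narrower scope appears twice, in the two places that say what the form will contain, so it is not an isolated slip. Section 3.8.1 is also a statement about consent. The documents therefore contradict each other, and neither reading can be dismissed.

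**Step 2. Look for other sources on prior treatment.** The baseline questionnaire in Section 3.7 takes drug treatment history by self-report. The NSMOS form, also self-report, is given at each assessment. It is described as covering services between study visits, with no look-back stated for baseline. Provider confirmation in Section 3.8.1 concerns MAT participation at and between assessments. Pre-enrollment CARES is thus the only source on prior treatment in the plan that is not self-report.

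**Step 3. Look for an analysis that uses it.** Sections 3.4 and 5.2 do not route CARES into the propensity score. The cost analysis in Section 5 takes utilization from participants. No section assigns the pre-enrollment records a role.

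**Step 4. Check the plan's design figure.** Inputs from Section 5.2: 25% vs 40%, 5% level (taken as two-sided), 80% power, correlation 0.3, 80% completers.

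- One time point: 152 per group.
- Two time points: 152 × (1 + 0.3)/2 = 152 × 0.65 = 98.8.
- Attrition: 98.8/0.8 = 123.5, so 124 against the stated 125.
- Power with 125 × 0.8 = 100 completers per group, effective n = 100/0.65: 80.5% against the stated 80%.

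The figure reproduces. It does not depend on the consent wording.

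**Step 5. Illustrate what an omitted confounder could do (assumed inputs).** Suppose that, after the listed covariates, recent City contact differs by 10 to 30 points between groups, and engagement differs by 10 to 20 points according to recent contact. The documents give neither figure.

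- Bias = prevalence difference × risk difference: 0.10 × 0.10 = 1 point, up to 0.30 × 0.20 = 6 points.
- SE = √(2 × 0.25 × 0.75/125 × 0.65) = 0.0442, or 4.4 points. All 125 per group count, because Section 5 classes missing as not engaged.
- Two-sided rejection rate with no true effect: 5.6% at 1 point of bias, 7.4% at 2, 10.4% at 3, 14.8% at 4, 27.4% at 6.

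The only related figures in the documents are in the Introduction: 41.4% of people who died of overdose had contact with the City's behavioral health system within 6 months of death, and 26.4% within 1 month. They describe decedents and any behavioral health contact. They suggest that recent contact is common but not universal, and they do not supply the inputs above.

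**The case against.** Several stronger readings are tempting, and the documents do not support them.

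- **That the consent covers only later records.** Section 3.8.1 says otherwise, and the forms are not available to check. Section 4.8.2 introduces the permission while explaining the need to confirm later treatment, so it may describe one purpose and not a limit. What stands is a conflict, not a proven gap.
- **That a planned baseline variable is lost to the adjustment.** The plan never routes CARES into the propensity score. Self-reported treatment history remains in both groups under either wording, and the Section 5.2 covariate list is open-ended. What could be lost is the chance to supplement or check a self-reported covariate.
- **That the consent wording raises the false-positive rate to 6–27%.** As the plan stands, that illustration would be identical under the broader wording, because CARES is in no model. It is a general calculation for unmeasured confounding, and its direction is unknown.
- **That the Section 8.4 list shows service records are unauthorized.** The list also omits HIV results, urine screens, liver tests, ASI and PHQ-9, all plainly collected. Its silence is weak evidence. It still needs to agree with whatever scope is chosen.
- **That the same records could verify the current-MAT exclusion at entry.** This would be a new screening step with no stated CARES turnaround, against the 1 or 2 days that Section 4.4's screening is followed by under Section 4.8.3. It is not recommended here.

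The objection that extra CARES variables are an enhancement and not the repair of an error has force. They are still worth adding, because the propensity score carries the whole burden of adjustment.

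**Conclusion.** The point holds as an internal contradiction with a practical consequence. The plan should settle the period covered by the CARES permission before enrollment, because the narrower choice can be reversed only by re-consent. It should also say what the pre-enrollment records are for. In a non-randomized comparison, the recency of City treatment contact is a plausible confounder that the named covariates do not capture.

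Neither sample size nor power changes. The size of any confounding cannot be computed from the documents: the 1 to 6 points of bias and the corresponding error rates rest wholly on the assumed residual differences. The practical harm depends on the forms following the narrower text, which cannot be verified. This is a change that should be made. It does not invalidate the design.

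**What to change.** 1. Before enrollment, change the CARES permission in Section 4.8.2 and in the comparison-group text of Section 4.9.1 to match Section 3.8.1, covering City services both before and after enrollment. Make the Section 8.4 authorization consistent with it.
2. In Section 5.2, state the data source for the count of previous treatments. Keep that self-reported count, and add to the propensity model, from CARES: any City behavioral health contact in the 6 months before enrollment; any MAT episode in the 12 months before enrollment; and an indicator for no CARES match.
3. Define these variables identically in both groups and exclude the index BAC/CRC visit. Otherwise every comparison participant would count as having recent contact by construction, and the variable would record group membership instead of history.

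The cost is one consent and authorization wording change, two derived history variables with a match indicator from a data pull the protocol already plans, and some participants whose records do not match.
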